2. OBJECTIVES

2.1 Primary objective:

1: To investigate the modifying effects of WHO-recommended sodium intake (90 mmol per day) vs. high sodium intake (targeted at 250 mmol per day) on the effect of ertugliflozin 15 mg daily, versus placebo, on 24-hour blood pressure in overweight/obese adults with type 2 diabetes.

2.2 Secondary objective:

To investigate the efficacy of ertugliflozin 15 mg daily, versus placebo, in overweight/obese adults with type 2 diabetes to reduce the hypertensive effects of a high-sodium diet (250 mmol per day) versus 24-hour blood pressure measurement during participant's normal diet (170 mmol/per day) obtained at screening visit.

[figure not shown]

3. STUDY DESIGN

The study is a bi-center randomized, placebo-controlled, crossover intervention study. Total number of included participants is 34, which undergo 4 conditions in randomized order (randomization list generated by computer and supervised by pharmacy; blinded to investigator). While the treatment will be blinded for all participants, the sodium interventions are open-label. Study design is shown in the figure below.

The 4 conditions are:

- 1) low-sodium diet; placebo
- 2) low-sodium diet; ertugliflozin 15 once daily
- 3) high-sodium diet; placebo
- 4) high-sodium diet; ertugliflozin 15 mg once daily

4. STUDY POPULATION

4.1 Population (base)

Participants will be recruited from the database at Amsterdam Diabetes Center at Amsterdam UMC and by advertisement in local papers. This database has currently over 500 individuals with diabetes that have agreed to be approached for new studies and that have been phenotyped in dept. University of Colorado has a similar database ensuring rapid inclusion of required participants.

4.2 Inclusion criteria

In order to be eligible to participate in this study, a subject must meet all of the following criteria:

- Adults with previously diagnosed T2DM according to American Diabetes Association (ADA) criteria
- HbA1c 6.5-10%
- Age 18 – 85 years of age
- Overweight or obese with BMI: $>25 \text{ kg/m}^2$
- We will make every effort to enrol participants of all races/ethnicities.”
- Both sexes (females must be post-menopausal; no menses >1 year; in case of doubt, Follicle-Stimulating Hormone (FSH) will be determined with cut-off defined as $>31 \text{ U/L}$)
- Ability to provide signed and dated, written informed consent prior to any study procedures
- Estimated GFR 60-90 ml/min/1.73m² by CKD-EPI matching the eGFR range of most participants in VERTIS-CV
- Sodium intake at baseline $< 200 \text{ mmol/day}$
- UACR $< 30 \text{ mg/mmol}$
- All participants need to be on a stable dose of diabetes medication, including Metformin, SU, DPP4-inhibitors, or insulin.
- Participants suffering from hypertension need to be on a stable dose of RAS inhibitors. In case RAS inhibition is not tolerated, the participant should be on a stable dose of other antihypertensive treatment.

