4.3 Exclusion criteria

A potential subject who meets any of the following criteria will be excluded from participation in this study:

- History of unstable or rapidly progressing renal disease

- Estimated GFR <60 mL/min/1.73m² or eGFR > 90 mL/min/1.73m² determined by CKD-EPI
- UACR > 30 mg/mmol
- Current/chronic use of the following medication: SGLT2 inhibitors, TZD, GLP-1RA, glucocorticoids, immune suppressants, antimicrobial agents, chemotherapeutics. Participants should be on a stable dose of antipsychotics, tricyclic antidepressants (TCAs) and monoamine oxidase inhibitors (MAOIs). Subjects on diuretics will only be excluded when these drugs cannot be stopped for the duration of the study.
- Chronic use of non-steroidal anti-inflammatory drugs (NSAIDs) will not be allowed, unless used as incidental medication (1-2 tablets) for non-chronic indications (i.e. sports injury, headache or back ache). However, no such drug can be taken within a timeframe of 2 weeks prior to renal testing
- History of diabetic ketoacidosis (DKA) requiring medical intervention (e.g. emergency room visit and/or hospitalization) within 1 month prior to the Screening visit.
- Current urinary tract infection and active nephritis
- Recent (<6 months) history of cardiovascular disease, including:
 - o Acute coronary syndrome
 - o Chronic heart failure (New York Heart Association grade II-IV)
 - o Stroke or transient ischemic neurologic disorder
- Severe hepatic insufficiency and/or significant abnormal liver function defined as aspartate aminotransferase (AST) >3x upper limit of normal (ULN) and/or alanine aminotransferase (ALT) >3x ULN
- Active malignancy. History of malignancy is allowed unless the participant still has active treatment other than hormonal therapy.
- History of or actual severe mental disease
- Substance abuse (alcohol: defined as >4 units/day)
- Allergy to any of the agents used in the study
- Individuals who are investigator site personnel, directly affiliated with the study, or are immediate (spouse, parent, child, or sibling, whether biological or legally adopted) family of investigator site personnel directly affiliated with the study
- Inability to understand the study protocol or give informed consent

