After confirmation of eligibility during screening, a 24-hr blood pressure measurement as well 24-hr sodium excretion is measured prior to the dietary blocks as detailed below. This 24-hr sodium and blood pressure measurement will be crucial for hypothesis 2. Urine containers and 24-hr blood pressure meters are provided to the patient and collected after recording.

Screening	Day 0	Day 1 (offered at home of participants to reduce travel)
Medical history	X	
Physical examination	X	
Review of medication	X	
Office blood pressure	X	
Routine hematology and chemistry	X	
HbA1c	X	
Urinary dipstick	X	
Start 24-hr urine sodium collection	X	
Start 24-hr BP measurement	X	
Return 24-hr urine sodium collection		X
Return 24-hr BP measurement		X

Subsequently, 4 of the blocks of 20 days below are conducted in random order with differences in study medication (placebo versus ertugliflozin) and sodium diet (90 mmol/day versus 250 mmol/day). The washout is 4 weeks between the blocks. Please refer to the figure on page 11. Urine containers are provided to the patients.

A sodium diet is commenced (either aimed at 90 mmol/day or 250 mmol/day) and it is expected that after 10 days this is reached (+/- 20%, due to normal variation in sodium excretion). This will be assessed with two 24 hour urine collections. Subsequently, the diet is continued and treatment with the study medication commences. In the morning of day 9, 24-hour blood pressure recording starts. At the study visit at day 10 of treatment, endpoints are collected following an overnight fast of 10-hours at our clinical trial unit as indicated below. A flow chart of study activities is attached below.

Subject will arrive at Amsterdam UMC location AMC for multimetric MRI following an overnight fast. Subjects are then brought to Clinical Research Unit (CRU) location VUMC where the 24-hour urine collection is processed (in order to assess sodium

excretion and other variables of interest obtained from 24-hr urine collection). The 24-hour blood pressure recording is stopped. Two intravenous catheters will be placed in both forearms for blood sampling and for the administration of test-agents (e.g. iohexol and PAH). A total of 125 mL blood will be drawn during the day for this purpose. The renal protocol commences with measurement of GFR and effective renal plasma flow (ERPF) based on continuous infusion for 2.5.

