During the infusion, several measurements will be performed including anthropometrics, bio-impedance analysis, blood pressure measurement and collection of samples for biomarker analysis.

	Day -10	Day -2	Day -1	Day 0	Day 3	Day 10
Start sodium-diet (continue until day 10)	X					
24-hr urine sodium (compliance)		X	X			
Start study medication (continue until day 10)				X		
Telephone call compliance					X	
Recent history						X
24-hr blood pressure						X
Measured GFR						X
ERPF						X
Intrarenal hemodynamic function						X
Office blood pressure						X
Hematocrit						X
Renal oxygenation (BOLD MRI)						X
RAAS components						X
Collection of biomarkers						X
Body anthropometrics						X
24-hr urine analysis (sodium, UACR)						X

Efficacy measurement more detailed:

- 1) **Height.** A height measuring board will be used to assess height. Patients will be asked to remove their footwear and headgear and to stand on the board with their feet together, heels against the back board and knees straight. The patient should be looking straight ahead, without tilting the head up, with eyes and ears at the same level. The measure arm will gently be moved down onto the head of the participant and height will be read in centimeters at the exact point.
- 2) **Weight.** Body weight will be recorded by a digital calibrated weighing scale on a firm, flat surface. Patient will be asked to remove their footwear, extra layers of clothing, jewelry and any items in his/her pockets before standing still on the weighing scale with arms placed on the side. Measurement will be recorded on the Case Report Form (CRF) to the nearest kilogram. No deduction for clothing will be permitted.
- 3) **Body Mass Index (BMI).** BMI will be derived from height and bodyweight by using the mathematical formula: $BMI = [kg/[m]^2]$.
- 4) **Waist circumference.** A constant tension tape will assess waist circumference with the patient in a standing position with the arms relaxed at the sides and without clothing, that is, directly over the skin. Measurement will be performed at the midpoint between the lower margin of the last palpable rib and the top of the iliac crest at the end of a normal expiration.

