- 5) **Body-impedance analysis.** To measure body fat content we will use the tetrapolar Soft Tissue Analyzer® (STA, Akern, Florence, Italy), which can perform Bio-Impedance Analysis (BIA). This technique measures the resistance in the body tissues when a 50 kHz AC electrical current is given between four electrodes. Resistance can be measured by placing two electrodes on the dorsal hand and two on the foot at the unilateral side of the body (Lukaski & Bolonchuk, 1988). Extracellular water (ECW) as a percentage of total body water (TBW) and body cell mass (BCM) will be calculated independent of weight and height.
- 6) **ECG:** A 12-leads ECG will be made in the fasting resting state during screening in order to assess cardiac conduction parameters. Heart rate on the ECG will be defined as the mean rate of 10 R-R intervals. PQ-time, QRS-time and QT-time will be calculated, QT-time will be corrected for heart rate by using the Bazett formula (C. Bazett, 2006). The cardiac vector and ECG morphology will be assessed.
- 7) **Blood pressure and heart rate (office):** Blood pressure and heart rate will be measured using an automatic oscillometric device (Dinamap®, GE Healthcare) After an acclimatization period of >5 minutes, blood pressure will be measured three times at the non-dominant arm, with the subject in a semi-recumbent position, using an appropriate cuff-size. The mean of the last 2 measurements will be used as final value (Mengden et al., 2010; Pickering et al., 2005).
- 8) **GFR** is measured by steady-state plasma iothexol concentrations measured at T=120 and T=150 as done in our previous approved protocols.

9) **ERPF** is measured by steady-state plasma PAH concentrations measured at T=120 and T=150 as done in our previous approved protocols.

10) **Filtration fraction** (GFR/ERPF) and renal vascular resistance (ERPF/mean arterial pressure) are calculated.

12) **24-hour blood pressure** is derived from Mobil-O-graph devices (24 ambulatory blood pressure monitors, The Netherlands), which will be available at both sites.

Daytime systolic blood pressure (SBP), daytime diastolic blood pressure (DBP), nighttime SBP, daytime DBP and nocturnal dipping pattern (in mmHg) are recorded.

12) sodium sensitivity is calculated as following: changes in blood pressure due to the high-sodium diet versus diet at screening (estimated based on experience/previous trials at ~165-170 mmol/day) and the effect on this parameter by ertugliflozin versus placebo.

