13) **Multiparametric MRI** will be carried out to measure additional kidney physiology parameters. The multiparametric MRI is performed on a tesla 3 machine. The MR examination will last 45 minutes maximum. During the scans, heart rate and blood pressure will be monitored. Patients get hearing protection in the form of ear-plugs and headphones. During the examination, they are in contact with the technicians via the intercom. Throughout the examination, patients will receive breathing instructions, for example to hold their breath for 20 seconds maximum, in order to produce accurate images. The MRI exam includes BOLD MRI to measure oxygenation, but also ASL and phase contrast MRI to obtain renal artery blood flow.

- BOLD-MRI: BOLD-MRI will be performed in order to measure renal tissue oxygenation. BOLD MRI exploits the difference in magnetic properties between oxygenated and deoxygenated hemoglobin (Prujm et al., 2018). Presence of deoxygenated hemoglobin will result in an accelerated signal decay on the BOLD images. Measurement of this signal decay results in a measure of the amount of deoxygenated hemoglobin, the apparent relaxation rate $R2^*$, which inversely relates to level of tissue oxygenation.

-ASL: In ASL, the blood travelling through the aorta is magnetically labeled before acquiring an image (the "label" image) (Odudu et al., 2018). Other images are acquired without any label (the "control" image). The difference between the label and control image will only be around 2%, so this procedure is repeated several times. The average difference between those images can be used to obtain a perfusion map of the kidney. Phase-contrast MRI is done to obtain renal artery blood flow.

14) **serum biomarkers**: hematocrit, serum albumin, plasma glucose and additional serum biomarkers are measured in the fasted state

15) **24-hour urine albumin and glucose excretion** is measured. Additional material for urinary biomarkers of interest such as markers of inflammation and electrolytes is stored.

16) **Safety and tolerability**: recent history and focused physical examination is carried out to assess potential adverse effects of study medication.

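### Eligibility sets no blood-pressure ceiling and requires no reading off diuretics, although every participant is assigned two 20-day high-sodium blocks

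*Combined protocol and SAP*

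**What the plan says.** **Entry.** Section 4.2: "Participants suffering from hypertension need to be on a stable dose of RAS inhibitors". If these are not tolerated, a stable dose of another antihypertensive is enough. Section 4.3 on diuretics: "Subjects on diuretics will only be excluded when these drugs cannot be stopped for the duration of the study". The two sections give numeric limits for HbA1c, eGFR, UACR, liver enzymes and alcohol, but none for systolic or diastolic pressure. Section 4.3 has no general clause allowing exclusion on the investigator's judgement.

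**Screening.** The section 8.3 table lists office pressure on Day 0. On the ambulatory baseline the text says: "After confirmation of eligibility during screening, a 24-hr blood pressure measurement as well 24-hr sodium excretion is measured prior to the dietary blocks". No cut-off is attached to either reading.

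**Within a block (8.3).** The diet starts on Day -10. Urine is collected on Days -2 and -1, tablets start on Day 0, and the Day 3 entry is "Telephone call compliance". Then: "In the morning of day 9, 24-hour blood pressure recording starts". At the day-10 visit office readings follow the stated method ("blood pressure will be measured three times at the non-dominant arm"), and for the MRI: "During the scans, heart rate and blood pressure will be monitored".

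**Between blocks.** "The washout is 4 weeks between the blocks".

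**Stopping.** Sections 5.3 (escape medication) and 8.4.1 (specific withdrawal criteria) are both marked not applicable. Section 8.4 provides for withdrawal on the investigator's judgement.

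**The concern.** The trial is built on the expectation that sodium raises pressure in these patients. The introduction describes type 2 diabetes as a sodium-sensitive state, the secondary objective concerns the hypertensive effect of the high-sodium diet, and section 13.1 accepts that pressure may rise. A stable dose says nothing about the level of pressure reached on that dose. For someone on a diuretic, entry removes a drug and then adds sodium. Age runs to 85, and acute coronary syndrome or stroke excludes only if it occurred within six months.

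The main stake is participant safety. There is also a statistical one. Anyone withdrawn later for high pressure drops out of the completers-only efficacy population (10.1) and is replaced (8.5), which selects on the primary endpoint after randomisation. Screening such a person out beforehand narrows the population but leaves the randomised comparison intact.

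**Working it through.** **1. The plan's own figures.** Day -10 to Day 10 is 10 - (-10) = 20 days, which matches the two 20-day high-sodium periods in section 13.1. Per participant that is 2 × 20 = 40 days. The sample size of 34 also reproduces: a paired t-test with standardised difference 4/8 = 0.5 and two-sided alpha 0.05 gives 80.8% power at n = 34 and 79.5% at n = 33. The sample size is not in dispute here.

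**2. Time to the first scheduled in-block reading.** Day 9 - (Day -10) = 19 days to the start of the ambulatory recording. Day 10 - (Day -10) = 20 days to the office reading.

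**3. Time off diuretics.** Four blocks of 20 days and three washouts of 28 days: 4 × 20 + 3 × 28 = 80 + 84 = 164 days from first block start to last block end. This is a minimum, because no text dates the stop.

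**4. Size of the sodium load.** Target 250 mmol/day against the stated usual intake of 170 (section 5.2): 250 - 170 = 80 mmol/day, and 80/170 = 47%. Section 4.2 requires baseline intake below 200, so the target exceeds every eligible participant's intake by more than 250 - 200 = 50 mmol/day.

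**5. Readings on file at the first block.** Two of the four conditions are high-sodium. If each condition is equally likely to come first (assumption), 34 × 2/4 = 17 participants start on high sodium with only screening readings available.

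**6. Eligibility trace.** Take a candidate on a stable RAS inhibitor plus a diuretic, within the HbA1c, eGFR and UACR limits, whose screening office pressure is severely raised.
- 4.2 hypertension rule: met, because the dose is stable.
- 4.3 diuretic rule: met, if the drug can be stopped.
- Remaining 4.2 and 4.3 criteria: none uses blood pressure.
- Reading after the diuretic is stopped: none required.

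The candidate is eligible, and the office reading already taken plays no part in that decision.

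**7. What cannot be computed.** The documents give no distribution of screening pressure, so neither the number of participants above a ceiling nor an event rate follows from them.

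**The case against.** The case for leaving the plan alone is substantial. Section 8.4 directs the investigator to end participation when continuing does not serve the participant, and lists adverse events as grounds. Staff can be reached 24 hours a day (11.3), and section 13.1 provides checks on complaint. Screening includes history, examination, medication review and an ECG. Recent cardiovascular events and eGFR below 60 are excluded, and section 9.2.2 records that the ethics committee regards the study as low-risk. An ambulatory recording precedes any diet block. The diuretic rule can itself be read as a clinical gate: a person who would be unsafe without the drug cannot stop it.

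This stands as mitigation. It does not fill the gap at entry: most of these safeguards act after enrolment or only if symptoms appear, and the diuretic rule requires no reading to show that stopping was safe.

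Three stronger readings are tempting, and the documents do not support them.
- *Nothing can stop a block.* Section 8.4 can. It works by judgement and sets no level.
- *95% of high-sodium exposure goes unobserved, so the risk is large.* The product 34 × 2 × 19 = 1,292 of 34 × 2 × 20 = 1,360 participant-days is just 19/20. It describes the schedule and measures no risk, and an entry ceiling leaves it unchanged.
- *The risk statements contradict each other.* The Summary and 11.3 promise close monitoring, while 13.1 describes checks on complaint. Scheduled day 9-10 readings and complaint-triggered checks can coexist, so aligning the text is a wording matter.

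**Conclusion.** The point holds as a gap in eligibility. As written, a treated but severely hypertensive person, or one newly off a diuretic with no reading since, may enter two 20-day high-sodium blocks. The sponsor should close this gap, because doing so changes who is exposed and uses a measurement already taken. Its size is the exposure per such person: 40 days at a target 80 mmol/day above stated usual intake, with the first scheduled reading 19 days into each block and, where a diuretic was stopped, at least 164 days off it. How many people this concerns is unknown and may be few.

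Confidence is medium. The design figure is not shown, so the schedule is taken from the text and tables of section 8.3. Investigators would probably act on an extreme reading, but the plan gives no level for doing so.

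**What to change.** **Main change, section 4.3.** Add an exclusion for screening office blood pressure above a numeric severe-hypertension ceiling set by the sponsor's clinicians. The documents give no value; a ceiling somewhere from 160/100 to 180/110 mmHg is an assumption for discussion. Apply it before randomisation, and repeat the reading after diuretics are stopped and before the first diet block. If the stop can be made before randomisation, a failed repeat is simply a screen failure. Office pressure is the practical choice because the 8.3 text places the ambulatory recording after eligibility is confirmed, although the screening table starts it on Day 0.

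**Optional, section 8.4.1.** Before each high-sodium block the investigator compares the screening 24-hour recording and any earlier day-10 recording with a prespecified severe level, and records continue or withdraw. The 28-day washout leaves time for this. Withdrawals here select on the primary endpoint and trigger replacement, so the level should be reserved for severe hypertension, and the number, block and reading of any withdrawal reported beside the per-protocol result.

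**Treatment changes.** A mid-crossover change of antihypertensive departs from the stable-dose rule and confounds the within-person 24-hour contrast. If one becomes necessary, record it as a protocol deviation and report its effect on the primary contrast.

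**Cost.** A protocol amendment, a few candidates screened out, and one extra office reading for each person who stops a diuretic.

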4.3 Exclusion criteria

A potential subject who meets any of the following criteria will be excluded from participation in this study:

- History of unstable or rapidly progressing renal disease

- Estimated GFR <60 mL/min/1.73m² or eGFR > 90 mL/min/1.73m² determined by CKD-EPI
- UACR > 30 mg/mmol
- Current/chronic use of the following medication: SGLT2 inhibitors, TZD, GLP-1RA, glucocorticoids, immune suppressants, antimicrobial agents, chemotherapeutics. Participants should be on a stable dose of antipsychotics, tricyclic antidepressants (TCAs) and monoamine oxidase inhibitors (MAOIs). Subjects on diuretics will only be excluded when these drugs cannot be stopped for the duration of the study.
- Chronic use of non-steroidal anti-inflammatory drugs (NSAIDs) will not be allowed, unless used as incidental medication (1-2 tablets) for non-chronic indications (i.e. sports injury, headache or back ache). However, no such drug can be taken within a timeframe of 2 weeks prior to renal testing
- History of diabetic ketoacidosis (DKA) requiring medical intervention (e.g. emergency room visit and/or hospitalization) within 1 month prior to the Screening visit.
- Current urinary tract infection and active nephritis
- Recent (<6 months) history of cardiovascular disease, including:
 - o Acute coronary syndrome
 - o Chronic heart failure (New York Heart Association grade II-IV)
 - o Stroke or transient ischemic neurologic disorder
- Severe hepatic insufficiency and/or significant abnormal liver function defined as aspartate aminotransferase (AST) >3x upper limit of normal (ULN) and/or alanine aminotransferase (ALT) >3x ULN
- Active malignancy. History of malignancy is allowed unless the participant still has active treatment other than hormonal therapy.
- History of or actual severe mental disease
- Substance abuse (alcohol: defined as >4 units/day)
- Allergy to any of the agents used in the study
- Individuals who are investigator site personnel, directly affiliated with the study, or are immediate (spouse, parent, child, or sibling, whether biological or legally adopted) family of investigator site personnel directly affiliated with the study
- Inability to understand the study protocol or give informed consent

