8.4 Withdrawal of individual subjects

Subjects can leave the study at any time for any reason if they wish to do so without any consequences. The investigator can decide to withdraw a subject from the study for urgent medical reasons. When participants decide to withdraw their participation, they will be asked to participate in 'early-term assessments'.

After subjects have entered the study, participation will be stopped in case of occurrence of any of the following:

- Participants own decision
- The occurrence of an AE or clinically significant laboratory change or abnormality that, in the judgment of the investigator, warrants withdrawal of the study
- Subjects need medical procedures that are not allowed in the protocol
- Subjects cannot undergo the procedures to investigate the research questions as outlined in this protocol
- Non-compliance
- In addition to these requirements for study drug discontinuation, the investigator should discontinue study participation for a given subject if, on balance, he thinks that continuation would be unbeneficial to the subjects well-being

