(incidence rate per 100 patient years 0.5) when proper instructions with respect to hygiene are provided, as will be done in our study. In addition, it is easily treated with a topical drug. The most feared side effect is euglycemic diabetic ketoacidosis (DKA). Due to lowering of endogenous or exogenous insulin levels, people with type 1 diabetes showed marked increases in euglycemic DKA despite controlled trial setting. For this reason, SGLT2 inhibitors are only in exceptional situations given to people with type 1 diabetes. In people with type 2 diabetes, euglycemic DKA is extremely rare, approximately 1 case per 1000 patient years. This likely concerns misclassified type 2 diabetes patients in whom insulin was stopped or reduced. To mitigate euglycemic DKA risk in our study, type 1 diabetes patients are excluded in our study, as well as individuals with diabetes and BMI <25 kg/m² as they phenotypically resemble type 1 diabetes patients. To prevent hypoglycemia, insulin dosages are lowered by the study team prior to initiation of the study drug if indicated. The study team consists of lead experts in the field of diabetology with ample experience in dosing glucose-lowering drugs. For the sodium diet we will monitor blood pressure when complaints are expressed by the study participant.

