13.2 Synthesis

Although there will be no medical benefit for participants of this study, we feel that the risk of the study protocol is moderate. The drug is well-tolerated in thousands and thousands of patient years with side effects being predictable, preventable and treatable. The effects of the sodium diet also do not pose a risk. In addition, the participants may receive education how to lower their sodium intake following study participation. The risk of the study procedures are low with placement of IV cannula as the most invasive study activity. Our previous protocols have demonstrated safety with respect to the imaging and kidney function tests.

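### Section 4.3 excludes previous DKA only if it fell in the month before screening, without a stated reason; removing the time limit is a cheap, optional safety improvement

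*Combined protocol and SAP*

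**What the plan says.** The only criterion that concerns past DKA is in section 4.3: "History of diabetic ketoacidosis (DKA) requiring medical intervention (e.g. emergency room visit and/or hospitalization) within 1 month prior to the Screening visit". Section 4.2 sets none. It asks for "Adults with previously diagnosed T2DM according to American Diabetes Association (ADA) criteria", BMI above 25 and HbA1c of 6.5 to 10%, and it states that "All participants need to be on a stable dose of diabetes medication", with insulin among the permitted drugs. It does not say how long the dose must have been stable.

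Section 13.1 j ranks euglycemic DKA as the adverse effect to be feared most. It puts the rate in type 2 diabetes at "approximately 1 case per 1000 patient years" and suggests that the cases are people wrongly labelled as type 2 whose insulin was withdrawn or cut. Its DKA safeguards are that "type 1 diabetes patients are excluded in our study, as well as individuals with diabetes and BMI <25" kg/m². The same paragraph allows the study team to reduce insulin before study drug where indicated, to avoid hypoglycaemia.

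Every participant who completes the crossover takes ertugliflozin for two blocks of 10 days (sections 8.7 and 11.3). Section 13.2 opens with "Although there will be no medical benefit for participants of this study".

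**The concern.** The protocol already accepts that a history of DKA is a reason to keep someone off the drug, but it disregards that history once a month has passed. Nothing in 4.3 or 13.1 says why a month is enough. Elsewhere in 4.3 the look-back is longer: six months for cardiovascular events, and no limit for unstable renal disease or severe mental disease.

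An earlier DKA is a plausible marker of the misclassified patient whom 13.1 j has in mind. The BMI rule is a proxy for the same problem, but a person with BMI above 25 and an earlier DKA passes it. The laboratory tests listed for screening in 8.3 include none aimed at diabetes type, so medical history is the main means of finding such a person.

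Only participant safety is at stake. The trial offers participants no medical benefit, so even a small avoidable risk of a serious event is worth removing if that costs little. As written, such a person is eligible by rule, and keeping them out depends on case-by-case judgement at two sites.

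**Working it through.** **What the criteria catch.** Take a person with a type 2 label, BMI above 25, a stable regimen, HbA1c of 10% or less, and a DKA treated in hospital just over a month before screening.

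- Section 4.3, DKA criterion: not met, because the event is outside the window.
- Section 4.2, type 2 diabetes by ADA criteria: excludes only if the diagnosis is itself doubted.
- Section 13.1 j safeguards (type 1 diabetes, BMI below 25): neither applies.

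No written rule excludes this person.

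**Earliest first active dose.** Inputs: 31 days from DKA to screening (just outside a month counted as 30 days); 0 days to confirm eligibility (the most extreme case); 1 day for the 24-hour urine and blood pressure recordings (8.3); 10 days of diet before the first tablet (8.3); blocks of 20 days with 4 weeks of washout between them (8.3).

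- Ertugliflozin block first: 31 + 0 + 1 + 10 = 42 days.
- Each earlier placebo block adds 20 + 28 = 48 days.
- One placebo block first: 42 + 48 = 90 days.
- Both placebo blocks first: 42 + 96 = 138 days.

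These are minimums, because no latest start for block 1 is set. Four conditions can be ordered in 24 ways: 12 start with ertugliflozin, 8 have one placebo block first and 4 have both. If all 24 were equally likely (an assumption, as the sequences are not listed), the three minimums would apply to 1/2, 1/3 and 1/6 of entrants.

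**Expected cases at the protocol's rate (1 per 1000 patient-years).**

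- Whole trial: 34 × 2 × 10 = 680 drug-days; 680 / 365.25 = 1.86 patient-years; 1.86 × 1/1000 = 0.0019 cases, about 1 in 537.
- One participant: 20 / 365.25 = 0.0548 patient-years; 0.0548 × 1/1000 = 0.000055, about 1 in 18,000.

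**If a previous DKA raises the risk.** The documents give no such rate. Purely as an assumed range, 10 to 100 times the stated rate gives 0.00055 to 0.0055 per such participant over 20 days (0.05% to 0.55%), against 0.0055% at the stated rate. The reduction from enrolling someone else instead would be 9 × 0.0000548 = 0.0005 to 99 × 0.0000548 = 0.0054 cases per person replaced.

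**Effect on the sample size.** The plan's figure reproduces. A paired t-test with difference 4, SD 8 and two-sided alpha 0.05 needs 34 completers (power 80.8%; 33 give 79.5%). The DKA criterion enters none of these inputs, so the figure is the same after the change.

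**The case against.** The strongest reply is that no benefit is shown. At the general rate, a person with an earlier DKA carries the same expected risk as whoever takes the place instead, so the change gains nothing unless past DKA raises risk on the drug. The documents never say that it does. This stands as far as size is concerned: any reduction is unquantified. It does not remove the direction, because the protocol itself treats recent DKA as an exclusion and links DKA to misclassified patients whose insulin is reduced, while admitting insulin users whose dose may be lowered.

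Other windows in 4.3 also come without reasons, and the protocol refers to an Investigator's Brochure that is not available here. That is fair: the absence of a reason in these documents does not prove that there is none.

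The 42-day figure is an extreme case. It needs same-day eligibility, although 8.3 allows up to two weeks to inform the participant. That also stands, and the figure is offered only as a lower bound.

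There are protections after entry: 10 days of diet before dosing, a day 3 telephone call, a day 10 history and examination, 24-hour access to staff, and an investigator who may stop a participant on judging that "continuation would be unbeneficial to the subjects well-being". They are real but partial. The day 3 call is for compliance, the examination comes at the end of dosing, and none of them decides who is eligible.

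Finally, a lifetime exclusion also removes people with a remote DKA of clear and resolved cause, and it does not reach a misclassified patient who has never had DKA. Both points are correct. They limit what the change can achieve.

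**Conclusion.** The point holds as an optional improvement. The one-month limit is unexplained in these documents, it leaves people with an earlier DKA eligible by rule, and the safeguards in 13.1 j do not cover them. It is not an error, contradicts nothing in the plan, and affects no endpoint, sample size or power figure.

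The size is very small: about 0.0019 expected cases across the trial at the protocol's own rate, and possibly no entrant with such a history at all. The case for acting rests on one clinical assumption that the documents support in direction but do not quantify, namely that past DKA marks a higher risk on ertugliflozin.

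**What to change.** In section 4.3, delete the closing time limit of the DKA criterion (from the word 'within' onward), so that any previous DKA requiring medical intervention excludes. The medical history taken at screening covers disease history, though 8.3 does not name DKA, so staff should ask about it directly. No new test or visit is needed. If the sponsor prefers to keep a limit, it should state the reason for the length chosen.

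The cost is one deleted phrase, possibly notified as a substantial amendment under 12.2, and the loss of candidates with a previous DKA. Their number is not given. The Amsterdam database alone holds over 500 people with diabetes before the other criteria apply, and Colorado has a similar one, for 34 places, so a material effect on recruitment is unlikely.
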